8.4.9 Selection and Timing of Dose for Each Subject

8.4.9.1 Dose Escalation Phase

The planned DLs to be investigated are presented in Table 2 below.

Table 2: Dose Levels for RGT100-PEI Dose Escalation

Dose Level	RGT100-PEI Dose	Volume of RGT100-PEI to be Injected
1	0.2 mg	1 mL
2	0.4 mg	2 mL
3	0.6 mg	3 mL
4	0.8 mg	4 mL

RGT100-PEI will be administered by intratumoral/intralesional injection. A dose escalation meeting with the SRC (refer to [Section 10.5](#) for SRC details) will be held to evaluate a dose escalation after all subjects in a DL per group have completed the DLT period.

Group A: Dosing for Group A (cutaneous lesions) will start first. The total dose will be administered each on 2 separate days of every week (Mondays and Thursdays or Tuesdays and Fridays) for a maximum of 4 weeks.

Group B: Dosing for Group B (liver lesions) will start once DL2 has proven to be safe in Group A. Dosing in Group B will then start at DL2. The total dose will be administered on 1 day of every week for a maximum of 4 weeks.

8.4.9.2 Expansion Phase

RGT100-PEI will be administered by intratumoral/intralesional injection at the RP2D established in the dose escalation phase.

The timing of dose administration will be as per the dose escalation phase.

8.4.9.3 Extended Treatment Phase

Subjects with PR or SD at 8 weeks and no clinical deterioration will be allowed to be treated with a second cycle of RGT100-PEI for an additional 4 weeks. This will be based on Investigator decision and subject agreement.

The selected dose and timing will be as per the recently completed previous treatment period in which subjects were enrolled. For details of study assessments to be performed for the extended treatment period, refer to [Appendix 17.1](#) (Group A) and [Appendix 17.2](#) (Group B).

8.4.9.4 Dose Modification and Dose Delay

Every effort should be made to administer trial treatment on the planned schedule. If a dose is missed, the dose should be administered as soon as possible. There should be at least 2 days between consecutive injections.

Treatments visits can be moved by 1 day when necessary for logistical purposes.

The End-of-Treatment Visit (Day 29) can be moved by ± 3 days and follow-up visits can be moved by ± 7 days when necessary.

The toxicity of treatment must be recorded before the administration of the next dose and graded according to the current version of the NCI CTCAE version 4.03. If individual

subjects experience treatment-related toxicity, subsequent trial treatment may be delayed as described below. Dose reductions are not permitted.

For grade 3, grade 4, or intolerable grade 2 toxicities, the treatment will be interrupted until recovery to \leq grade 1 or to baseline. Trial treatment will be permanently discontinued if the subject fails to recover to this extent within 3 weeks. Dose reductions or modifications are not allowed in both, the dose escalation and expansion phase.

If a subject cannot tolerate treatment despite the dose delays, trial treatment will be discontinued. The subjects will then undergo end of treatment visit and will be followed up according to plan.

In the event of a RGT100-PEI overdose (defined as any dose above the applicable DL), the Investigator should report such an overdose via the SAE form immediately and closely monitor the subject for AEs. The Investigator will use clinical judgement to treat any overdose.

Treatment is to be discontinued prematurely in the following situations:

- Complete response
- All injectable lesions have disappeared
- Intolerance of study treatment
- Subject withdrawal

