8.4.7 Dose-limiting Toxicity

The DLTs and MTD are defined using the NCI CTCAE version 4.03.

Dose-limiting toxicities will be drug-related toxicities (considered related or possibly related to) and graded using NCI CTCAE version 4.03 occurring during the DLT period and include:

- Non-hematologic toxicity \geq grade 3 (except diarrhea, nausea, and vomiting unless lasting >3 days despite optimal supportive care)
- Confirmed (with a second measurement after 24 hours) non-hematologic appropriately graded laboratory findings of grade ≥ 3 that were \leq grade 1 at baseline
- Hematologic toxicity:

- Grade 4 neutropenia ≥ 5 days, or grade 3 neutropenia with fever (fever is $> 38.4^{\circ}\text{C}$)
- Grade 4 thrombocytopenia, or grade 3 thrombocytopenia lasting > 7 days or with bleeding
- Any other toxicity assessed as related to RGT100-PEI, and which, in the opinion of the study Investigator(s) and the Sponsor physician constitutes a DLT

The DLT period will be 4 weeks. Evaluation of the available safety data over this DLT period will be required from at least 3 subjects per DL and per Group (A or B) before a decision is made whether to enroll additional subjects at the same, or the next DL.

Note: Subjects withdrawn from the study before the completion of the DLT period for reasons other than DLT will be replaced.

During dose escalation, escalation to the next DL will occur only if the safety and tolerability (including DLTs) data are acceptable as determined during the dose escalation meetings by the SRC. If any change is made to the grade or causality of an AE during the study that may alter its DLT status, the Sponsor and SRC must be informed immediately as this may affect dose escalation decisions.

The following toxicities will not be considered as DLTs:

- Grade 3 AE of tumor flare (defined as local pain, irritation, or rash localized at sites of known or suspected tumor)
- Grade 3 irAE that resolves to grade ≤ 1 within 7 days.

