10.4 Safety Variables

10.4.1 Adverse Events

10.4.1.1 Adverse Event Definition

An AE is defined as any untoward medical occurrence in a clinical study subject administered a medicinal product which does not necessarily have a causal relationship with this treatment. An AE can therefore be any unfavorable and unintended sign (including an abnormal laboratory finding), symptom, or disease temporally associated with the use of a medicinal (investigational) product, whether or not it is related to the medicinal (investigational) product. This includes an exacerbation of pre-existing conditions or events, intercurrent illnesses, drug interaction or the significant worsening of the indication under investigation that is not recorded elsewhere in the eCRF under specific efficacy assessments. Anticipated fluctuations of pre-existing conditions, including the disease under study that do not represent a clinically significant exacerbation or worsening need not be considered AEs.

The Investigator will monitor each subject for clinical and laboratory evidence of AEs on a routine basis throughout the study. Should an Investigator become aware of any study drug-related SAEs following this period these must also be reported as stated in [Section 10.4.4.3](#). Adverse event monitoring starts from the time the subject consents to the study until they complete the trial. All reportable AEs will be followed to a satisfactory conclusion. Any reportable drug-related AEs that are unresolved at the follow-up visit are to be followed up by the Investigator until resolution or stabilization.

AEs will be elicited by asking the subject a non-leading question, for example, “Have you experienced any new or changed symptoms since we last asked/since your last visit?” AEs should be reported on the appropriate page of the eCRF.

Each separate AE episode must be recorded. For example, if an AE resolves completely or resolves to baseline and then recurs or worsens again, this must be recorded as a separate AE. For AEs to be considered intermittent, the events must be of similar nature and severity.

Tumor progression is not an AE. However, the medical conditions associated with disease progression must be documented as AE.

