10.4.4.3 Reporting of Serious Adverse Events

SAEs must be reported from signing the informed consent up to and including 30 respectively 60 days after administration of the last dose, whether or not considered to be related to the investigational product.

Any SAE must be reported by the Investigator on a SAE Reporting Form **within 24 hours** of Investigator's awareness to **INC Research Safety & Pharmacovigilance**:

Email: ^{PPD} [REDACTED]

Fax: ^{PPD} [REDACTED]

The 4 minimum criteria for a valid SAE report include:

- Site identifier
- Subject identifier
- Event term
- Study drug

The Investigator should not wait to receive additional information to document fully the event before notification of a SAE. As soon as the 4 minimum mentioned above criteria are fulfilled, the Investigator must report the SAE within 24h of awareness. In addition, all further information requested on the SAE Reporting Form should be completed and sent to INC Research Safety & Pharmacovigilance as soon as possible. If the SAE has not been reported within the specified timeframe, a reason for delay must be provided when sending the SAE Reporting Form.

Where applicable, information from relevant laboratory results, hospital case records, and autopsy reports should be obtained and reported to INC Research Safety & Pharmacovigilance as soon as possible as well.

Instances of death, congenital abnormality, or an event that is of such clinical concern as to influence the overall assessment of safety, if brought to the attention of the Investigator at any time after cessation of study drug administration and linked by the Investigator to this study, should be reported to the study monitor.

Any laboratory values considered clinically significant or meeting grade 4 (NCI CTCAE) or above should be considered AEs and should be captured in the eCRF. Any events reported that also meet the SAE criteria should be reported in line with SAE reporting requirements.

All SAEs reported to INC Research Safety & Pharmacovigilance will be processed according to internal standard operating procedures (SOPs). INC Research Safety & Pharmacovigilance may request additional information for any SAE as judged necessary.

Any SAE occurring at any time after completion of study treatment or after the designated follow-up period that the Investigator consider to be related to any study drug must be reported to the Sponsor/INC Research.

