10.5 Safety Review Committee

The Safety Review Committee (SRC) will be composed of but not limited to the Principal Investigator(s), CRO Medical Monitor, Sponsor representative and Investigators and/or representatives from participating sites where possible. Additional experts or persons, both non-voting, may participate as needed.

The SRC will meet when all the subjects in each individual dose cohort have been treated and followed for the specified time, as defined in the study protocol for the safety assessments or sooner, if a significant safety issue arises. Following a thorough review of the available safety information by the SRC from the cohort and any new safety information from the preceding cohorts, the decision will be taken whether or not to increase the dose of the product for the next cohort. The SRC will thus meet after 3-6 subjects in a cohort have completed 4 weeks of treatment to evaluate the safety and initial efficacy data and decide on the next dose escalation. Minutes of these meetings will be taken and the recommendation from the SRC in relation to the dose increment will be recorded. Details of the organization, content and procedures of these dose escalation meetings and functioning of the SRC will be described in the SRC Charter.

Bi-Weekly Safety Calls will be held in addition to Dose Escalation Meetings during the dose escalation phase. INC Research will organize the Bi-Weekly Safety Calls and the Dose Escalation /SRC Meetings. The Bi-Weekly safety calls will commence approximately two weeks after the first subject is dosed at the first site. The SRC/Dose Escalation Meetings will be held upon completion of at least 3 evaluable subjects on each dose level (and additionally as required and agreed) during the pre-scheduled bi-weekly calls - ie the Bi-Weekly Safety Calls will serve as Dose Escalation Meetings when appropriate. Selected members of Rigontec and INCR teams will join during the Bi-Weekly Safety Calls. During the Dose Escalation Meetings, the aim is for the full SRC to be present. It is critical for the investigator of an active site to be in attendance during these safety meetings. The timing for the Dose Escalation Meetings will be fixed when the 3rd subject in a cohort has received their first

dose, and as appropriate depending on the SRC agreement on further subjects enrolled in cohort(s), if any. The meeting agenda, as well as listings of the safety data of the subjects, will be distributed prior to the call.

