11.1.2 Datasets or Populations Analyzed

All subjects enrolled in the study will be accounted for. The number of subjects who were NE, who died, or who withdrew before treatment began will be recorded. All subjects who received at least 1 dose of the study drug will be included in the analysis for toxicity.

Two subject populations will be used for the analyses:

- The safety population will consist of all enrolled subjects who received at least 1 dose of RGT100-PEI.
- The evaluable population will consist of all enrolled subjects who complete Week 4 or withdraw early for experiencing a DLT.

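### The symmetric visit windows let scheduled safety assessment end before the DLT and SAE periods do (End-of-Treatment on Day 26; follow-up at 23 or 53 days)

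*Combined protocol and SAP*

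**What the plan says.** Section 8.4.9.4 sets the windows: "The End-of-Treatment Visit (Day 29) can be moved by ± 3 days and follow-up visits can be moved by ± 7 days when necessary". The headers of Tables 3 and 4 repeat them. The same section adds: "Treatments visits can be moved by 1 day when necessary for logistical purposes".

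The periods themselves are stated in time:

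- **DLT period (8.4.7):** "The DLT period will be 4 weeks".
- **Escalation meeting (8.4.9.1):** held "after all subjects in a DL per group have completed the DLT period". Section 10.5 has the Safety Review Committee (SRC) meet "after 3-6 subjects in a cohort have completed 4 weeks of treatment".
- **Evaluable population (11.1.2):** "all enrolled subjects who complete Week 4 or withdraw early for experiencing a DLT".
- **SAE reporting (10.4.4.3):** "SAEs must be reported from signing the informed consent up to and including 30 respectively 60 days after administration of the last dose".

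The rules for other adverse events are mixed. Section 9 and Section 10.4.1.7 promise 30 days of follow-up, or 60 without progression. But Section 10.4.1.7 also ends observation of AEs that are neither serious nor related at the last study visit. The footnotes to Tables 3 and 4 limit AE capture after Week 9 to new, possibly related events. Section 10.4.1.1 says: "Adverse event monitoring starts from the time the subject consents to the study until they complete the trial".

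**The concern.** A 3+3 decision treats every evaluable subject as having been assessed over the same 4 weeks. Several DLTs in Section 8.4.7 are laboratory findings, which may cause no symptoms and are then found only if a sample is taken. If the last scheduled sample can precede the end of the period, a subject can be counted as free of DLT with its last days untested. With 3 to 6 subjects per dose level, one missed DLT can change the decision. Section 10.5 fixes the date of the escalation meeting when the third subject receives the first dose, and nothing requires a check on Day 28 beforehand.

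After treatment, treatment-related AEs and SAEs are primary endpoints (Section 7.2). If the closing visit can fall a week before or after its nominal day, the length of scheduled observation depends on visit logistics.

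**Working it through.** **1. The plan's own day.** The start of the DLT period is not given as a study day; I assume Day 1, the first injection. Then 4 × 7 = 28, the period covers Days 1-28, and the nominal End-of-Treatment visit on Day 29 (28 + 1) is the first day after it. The nominal schedule is consistent.

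**2. What the windows allow.**

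- End-of-Treatment: 29 ± 3 = Days 26-32. At the early limit, Days 27-28 remain.
- 30-day visit: 30 ± 7 = 23-37 days after the last dose. At the early limit, 7 of 30 days remain (23%).
- 60-day visit: 60 ± 7 = 53-67 days. At the early limit, 7 of 60 days remain (12%).
- Spread between subjects: 37 − 23 = 14 days, and 67 − 53 = 14 days.

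**3. Distance from the last injection.**

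- Group A (injection 8 on Day 25): 26 − 25 = 1 day, against a nominal 29 − 25 = 4.
- Group B (injection 4 on Day 22): 26 − 22 = 4 days, against a nominal 29 − 22 = 7. Four days is the spacing that Group A has on its nominal schedule.

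**4. What else is scheduled in Group A after injection 8 (Table 3).** Safety laboratory samples are taken on Days 1, 4, 8, 11, 15 and 22, with none on Day 25. Physical examination and ECOG status are last recorded on Day 22. No ECG is scheduled between screening and End-of-Treatment. Day 25 has vital signs to 4 hours, and PK and cytokine samples to 24 hours. The next visit is at 25 + 30 ± 7 = Days 48-62 (Group B: 22 + 30 ± 7 = Days 45-59). End-of-Treatment is therefore the only laboratory, examination and ECG assessment between injection 8 and Day 48 at the earliest.

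**5. How much this could move escalation.** This is an illustration, not a figure from the plan. It assumes a constant DLT hazard over 28 days, every subject seen on Day 26, and no DLT on Days 27-28 ever found. For true 28-day risk p, the observed risk is q = 1 − (1 − p)^(26/28). Under Table 1 of the protocol, P(escalate) = (1 − p)³ + 3p(1 − p)² × (1 − p)³.

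- True risk p = 0.30: 0.343 + 0.441 × 0.343 = 0.494.
- Observed risk q = 1 − 0.70^(26/28) = 0.282: 0.370 + 0.436 × 0.370 = 0.532.
- Rise: 3.7 percentage points. At p = 0.10 it is 1.1 (0.906 to 0.917), at p = 0.33 it is 3.8 (0.434 to 0.473), and at p = 0.50 it is 3.0 (0.172 to 0.202).
- Sensitivity: if Day 26 itself also goes unobserved (3 days lost), the rise is 1.6 to 5.9 points over the same range.

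**6. Late-only windows of the same size on the late side.** End-of-Treatment would fall on Days 29-32 and follow-up at 30-37 and 60-67 days. No visit would precede the end of its period, and the follow-up spread would halve from 14 to 7 days without vanishing.

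**The case against.** The strongest reply is that visits do not close these periods. The DLT and SAE periods are set in weeks and days, and the escalation meeting and evaluability depend on completing the 4 weeks. A subject seen on Day 26 has not completed the DLT period, and an event on Day 27 remains reportable. A reader might infer that the DLT and AE windows are cut short. For the DLT and SAE periods the documents do not support that, because nothing in them makes the visit the end of either period.

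Other safeguards also count:

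- Bi-weekly safety calls run throughout escalation.
- SAEs are reported within 24 hours of awareness, without needing a visit.
- Related AEs are followed until they resolve or stabilise, and related SAEs are reportable at any later time.

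Three tempting extensions also fail:

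- **Same-day visit.** Injection 8 could move to Day 26 and coincide with End-of-Treatment. But its 24-hour PK and cytokine samples would bring the subject back on Day 27, so zero days' spacing cannot be combined with no scheduled contact on Days 27-28.
- **The long gap.** The window does not create it. The nominal Group A interval from Day 29 to Day 55 is 26 days, longer than the 22 from Day 26 to Day 48.
- **The 23-day limit.** It ends in-study visits only for subjects who have progressed; the others continue to the 60-day visit.

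These points narrow the concern without removing it. Calls and spontaneous reports find symptomatic events. They do not supply a safety laboratory sample after Day 26, and the 24-hour PK and cytokine contact is not one.

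**Conclusion.** The point holds as a gap in scheduled ascertainment. In Group A, the one full assessment after the last injection may be held about 1 day after it with two DLT days still to run, so a laboratory DLT arising later may not be known when the SRC decides. In Group B the effect is weak.

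The effect on escalation is modest. With Days 27-28 wholly unobserved, the chance of escalating rises by 1.1 to 3.8 points for true DLT risks of 0.10 to 0.50. This rests on a constant hazard and on every subject being seen early, which is pessimistic because the windows apply only when needed. If toxicity clusters just after an injection, the figure for Group A could differ.

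In follow-up, a progressor seen at 23 days or a non-progressor seen at 53 has no later scheduled safety contact in the study, although SAEs are due for 7 more days. For other AEs the text is unsettled: the rules tied to the last visit, Week 9 and trial completion do not agree with the promised 30/60 days.

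**What to change.** 1. **End-of-Treatment window.** In 8.4.9.4 and the headers of Tables 3 and 4, make it late-only (Day 29, 0/+3) for dose-escalation subjects who complete treatment. Exempt subjects who discontinue early, whom 8.4.9.4 sends to this visit when they stop.
2. **Link to the decision.** Have the results of this visit available to the SRC before the subject counts as having completed the DLT period; a late-only window does not ensure this by itself. Because Day 29 lies just outside Days 1-28, also state the day the period starts and whether a finding first seen at this visit counts towards it.
3. **Follow-up visits.** Make them late-only (0/+7), or document a telephone AE/SAE contact at day 30 or 60 when the visit is held early.
4. **Equal observation.** Late-only windows still leave 30-37 and 60-67 days. For the primary AE summaries, count events to a fixed day after the last dose, for example day 30, which progressors and non-progressors would both be scheduled to reach.
5. **Reconcile the wording.** Align 10.4.1.1, the last-visit rule in 10.4.1.7 and the Week 9 footnotes of Tables 3 and 4 with the 30/60 days in Section 9, 10.4.1.7 and 10.4.4.3.

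Appendices 17.1 and 17.2 need no change to an End-of-Treatment window, since they carry none. The cost is slightly less scheduling freedom for sites and an occasional telephone contact. No subject, sample or clinic visit is added.

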6.6 Potential Risks and Benefits

Given that RGT100-PEI has not yet been tested in humans and this is a first-in-human study, the potential side effects of injecting this drug into humans are unknown. To date, RGT100-PEI has shown an acceptable safety profile for intratumoral/intralesional injection in animals. There has been a lack of any major side effects or toxicities in animal treated with RGT100-PEI.

Potential risks associated with the administration of RGT100-PEI based on nonclinical data may include the following:

- Immune-related adverse events (irAEs) (including colitis, hepatitis, thyroid complications) based on the fact that the mode of action of RGT100 revolves around the immune system
- Hypersensitivity reactions at the injected tumor site (skin rashes, pruritus or urticarial, flu-like symptoms such as fever, chills, muscle aches, fatigue, and headache, diarrhea, nausea and vomiting and low blood pressure)

- Altered liver function (increases in alanine transaminase [ALT], aspartate transaminase [AST], and lactate dehydrogenase [LDH], decreases in erythrocyte counts, hemoglobin levels, and hematocrit)
- Local reactions at the injected tumor site (swelling, induration, and erythema)

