8.4 Investigational Products

8.4.1 Investigational Products Administered

RGT100-PEI is to be administered by intratumoral/intralesional injection into cutaneous, subcutaneous, nodal and or intrahepatic lesions that are visible, palpable or detectable by imaging guidance (eg, ultrasound).

In Group A: RGT100-PEI will be administered into cutaneous, subcutaneous or nodal lesions by trained site staff.

In Group B: RGT100-PEI will be administered into liver lesions under image guidance (eg, ultrasound) by a radiologist or another experienced physician.

There will be no interruption between treatments, except as described in the dose modification and dose delay section ([Section 8.4.8.4](#)).

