9 TIMING OF STUDY PROCEDURES

Participants will undergo a screening period of up to 3 weeks. The study treatment period will be approximately 4 weeks (shorter if the subject withdraws, and longer if there are delays to dosing due to toxicities). All subjects will be followed up for 30 days following their final dose of RGT100-PEI or until resolution or stabilization of all treatment-related AEs, whichever is later. If no progressive disease (PD) is seen after a 30-day follow-up period, subjects will be in follow-up for another 30 days (total of 60 days after last injection), which defines the end of the trial. Further survival follow-up will be performed every 3 months for a period of 24 months outside of the main study.

Subjects will provide written informed consent before any study-related procedures are performed. The timing of study assessments is provided in Table 3 for Group A and Table 4 for Group B.

Table 3: Group A (Cutaneous) Schedule of Assessments

Trial Visits, Investigations, and Interventions	Screening	Treatment Period								End-of- Treatment Visit	Follow-up Visit		
	Day -21 to Day -1	Week 1		Week 2		Week 3		Week 4		Week 5	Week 9	Week 13 ^a	
		Day 1 Inj 1	Day 4 Inj 2	Day 8 Inj 3	Day 11 Inj 4	Day 15 Inj 5	Day 18 Inj 6	Day 22 Inj 7	Day 25 Inj 8	Day 29 (±3 days)	30 days after last injection (±7 days)	60 days after last injection (±7 days)	
RGT100-PEI injection ^a		+	+	+	+	+	+	+	+				
Informed Consent	+												
Medical History	+												
Eligibility Criteria	+												
Pregnancy Test ^b	+									+			
ECG	+									+	+	+	
Physical Examination ^c	+	+		+		+		+		+	+	+	
ECOG Performance Status	+	+		+		+		+		+	+	+	
Vital Signs ^d	+	10+	10+	5+	5+	5+	5+	5+	5+	+	+	+	
Overnight observation		+	As deemed appropriate by the investigator										
Height/Weight	+												
Hematology ^e	+	++	+	++	+	++		++		+	+	+	
Clinical Chemistry ^e	+	++	+	++	+	++		++		+	+	+	
Urinalysis ^e	+	++	+	++	+	++		++		+	+	+	
Autoimmunity ^f	+					+				+	+		
Infectious Diseases ^g	+									+	+		
Immunoglobulins ^h	+					+				+	+		
Immuno-monitoring ⁱ	+	+++							+++	+	+	+	
PK (RGT100-PEI) ^j		7+							7+				
Mutation Status ^k	+												
Tumor Assessment and Photography ^l	+	+		+		+		+		+	+	+	

Trial Visits, Investigations, and Interventions	Screening	Treatment Period								End-of- Treatment Visit	Follow-up Visit	
	Day -21 to Day -1	Week 1		Week 2		Week 3		Week 4		Week 5	Week 9	Week 13 ^a

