10.4.3 Monitoring of Hypersensitivity Reactions, Tumor Spread and Tumor Lysis

Subjects should be observed closely for hypersensitivity reactions and local reactions of the injected tumor site. Blood pressure, pulse, respiration rate, temperature and oxygen saturation should be monitored at the timepoints specified in Table 3 and Table 4. For the first 2 injections the minimum observation period will be 6 hours, and for subsequent injections, the minimum observation period will be 4 hours.

Hypersensitivity to RGT100-PEI is a potential safety risk in general as for any drug. There are no signs from nonclinical work that this may be expected. Hypersensitivity reactions should be dealt with according to local policy. Treatment will be permanently discontinued in the case of grade 3 or 4 hypersensitivity reaction.

A risk of tumor spread from an intratumoral injection has been proposed. However, tumor growth along needle tracks has generally been described only in circumstances where no anti-cancer agent is being administered. In therapeutic trials of intratumoral injection tumor dissemination has not been dose limiting nor reported as a clinically significant event. Injection sites will be carefully monitored throughout subject participation in the trial and any evidence of tumor growth along injection tracks reported as an AE of special interest. So far no data of relevant tumor cell spread have been publically reported from other agents which are intratumorally applied.

Generally there is also the potential risk for tumor lysis, however there are relatively few reports of tumor lysis syndrome in solid tumors. Potential risk factors include disease bulk, aggressive growth, hepatic involvement, and pre-treatment laboratory abnormalities such as elevated lactate dehydrogenase, uric acid, and creatinine. Investigators should be aware of this potential risk and routine measures should be taken for prevention and management.

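### Section 8.4.9.4 lets dosing resume after a resolved grade 3 or 4 hypersensitivity reaction, which section 10.4.3 requires to be a permanent stop

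*Combined protocol and SAP*

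**What the plan says.** Section 8.4.9.4 (Dose Modification and Dose Delay) sets the general rule for treatment-related toxicity: "For grade 3, grade 4, or intolerable grade 2 toxicities, the treatment will be interrupted until recovery to" grade 1 or lower, or to baseline. It continues: "Trial treatment will be permanently discontinued if the subject fails to recover to this extent within 3 weeks". It also stops treatment for a subject who cannot tolerate it despite delays. On dose it says: "Dose reductions are not permitted". The section closes with a list introduced by "Treatment is to be discontinued prematurely in the following situations", which has four items: complete response, disappearance of all injectable lesions, intolerance of the study treatment, and subject withdrawal. Hypersensitivity is not among them, and nothing in the section refers to 10.4.3.

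Section 10.4.3 (Monitoring of Hypersensitivity Reactions, Tumor Spread and Tumor Lysis) states: "Treatment will be permanently discontinued in the case of grade 3 or 4 hypersensitivity reaction". It gives no recovery window and no condition.

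Two other places send the reader to the dose-delay rule or rely on it. Section 8.4.1 says "There will be no interruption between treatments, except as described in the dose modification and dose delay section", and section 9 allows the treatment period to be "longer if there are delays to dosing due to toxicities".

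**The concern.** The two sections prescribe different actions for the same event. A treatment-related grade 3 or 4 hypersensitivity reaction falls within the wording of 8.4.9.4, which makes resumption depend only on recovery. Section 10.4.3 rules resumption out.

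The section with the wrong action for this event is the one a site is most likely to open when deciding whether the next injection goes ahead. It also leans towards dosing: it asks for every effort to keep to schedule and for missed doses to be given as soon as possible. The permanent stop is a single sentence in a safety-monitoring section.

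What is at stake is rechallenge after a severe reaction in a first-in-human trial. Section 6.6 lists "Hypersensitivity reactions at the injected tumor site" among the potential risks, and section 8.4.14 requires resuscitation facilities at each injection because of severe hypersensitivity. A secondary effect is on data. Treatment discontinuation due to treatment-related AEs is a primary endpoint (section 7.2), and sites applying different rules to the same event would record it differently.

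**Working it through.** The plan states no figure on this point, so there is nothing to reproduce. The check has two parts: comparing the text, and counting the injections exposed.

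**The two rules side by side, for a treatment-related grade 3 or 4 hypersensitivity reaction**

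| Course of the reaction | 8.4.9.4 read alone | 10.4.3 |
|---|---|---|
| Recovers to grade 1 or lower, or baseline, within 3 weeks | Interrupt, then resume at full dose | Permanent stop |
| Does not recover within 3 weeks | Permanent stop | Permanent stop |

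The rules agree in the second row and conflict in the first.

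**Does other text supply the missing exception?**

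- The intolerance item in the 8.4.9.4 list is undefined. The nearest wording in that section concerns subjects who cannot tolerate treatment despite delays. That presupposes a delay has been tried, which 10.4.3 does not allow.
- Section 8.3.4.1 lets subjects stop for AEs that the investigator judges incompatible with continuing. This is permissive.
- Section 8.2 has the investigator check that the dose is tolerated before further dosing. This is also a matter of judgement.
- Section 8.4.12 requires a permanent stop when steroids above the permitted dose are needed and there is no alternative. It applies only if the reaction is treated that way.
- Section 8.4.7 defines DLTs for escalation decisions. It does not say that a subject with a DLT must stop treatment.
- Section 10.4.4.3 requires SAEs to be reported within 24 hours. It gives no dosing instruction.

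None of these states that a resolved grade 3 or 4 hypersensitivity reaction is a permanent stop.

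**Injections exposed**

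Inputs: 8 planned first-cycle injections in Group A (Table 3) and 4 in Group B (Table 4). If the reaction follows injection k, the planned injections remaining are:

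- Group A: 8 − k, from 8 − 1 = 7 down to 8 − 8 = 0.
- Group B: 4 − k, from 4 − 1 = 3 down to 4 − 4 = 0.

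Under 10.4.3 the number is 0 for every k.

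These are upper bounds, because section 8.4.9.1 caps dosing at 4 weeks. Suppose that cap is read as a calendar limit, the reaction is on Day 1 and recovery takes the full 3 weeks. Dosing could then resume on Day 1 + 21 = Day 22. The remaining scheduled days would be Days 22 and 25 in Group A (2 injections) and Day 22 in Group B (1 injection). Section 9, which allows a longer treatment period after toxicity delays, points towards the higher figures.

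**The case against.** The strongest reply is that the correct rule exists, is mandatory, and sits in the section whose title names hypersensitivity. A general rule alongside a specific one is ordinary drafting, and a site that stops treatment complies with both. On that view this is only a missing cross-reference. Section 8.4.1 speaks of interruptions and does not make 8.4.9.4 the sole home of permanent stops. Others already sit elsewhere, for pregnancy (8.3.4.3) and prohibited steroids (8.4.12), so sites must look beyond it anyway. Section 8.4.9.4 requires toxicity to be graded before each dose. A related non-hematologic toxicity of grade 3 or higher is generally a DLT reviewed by the Safety Review Committee, and grade 4 events are SAEs. Section 10.4.3 also says that nonclinical work gives no sign that hypersensitivity should be expected.

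Much of this stands. Section 10.4.3 should govern, the discontinuation list is not a complete register of stops, and the safeguards make an actual rechallenge less likely. The injection counts are ceilings that need an early reaction, recovery in time and a site that misses 10.4.3. The rule in 8.4.9.4 is also limited to treatment-related toxicity.

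What does not stand is the claim that nothing in 8.4.9.4 is wrong. Its wording covers this event and prescribes resumption on recovery. The safeguards rest on judgement, depend on a particular treatment being used, or notify other people; none corrects the instruction.

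**Conclusion.** The concern holds. For a treatment-related grade 3 or 4 hypersensitivity reaction that resolves within 3 weeks, 8.4.9.4 as written gives an action contrary to 10.4.3, and the section has neither an exception nor a reference.

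The exposure runs from 0 to 7 further full-dose first-cycle injections per affected subject in Group A and from 0 to 3 in Group B, against none under 10.4.3. This assumes that a site follows 8.4.9.4 alone and that the planned injection count is completed after the delay. How many subjects might be affected cannot be estimated from the documents.

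Confidence in the textual conflict is high. The defect should be corrected on safety grounds and for consistent recording of discontinuations. It does not affect the sample size, the error rates or the 3+3 escalation rule.

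**What to change.** In section 8.4.9.4, add an exception to the interruption rule along these lines: except for grade 3 or 4 hypersensitivity reactions, for which treatment is permanently discontinued (see Section 10.4.3). Add grade 3 or 4 hypersensitivity as an item in the premature-discontinuation list of the same section. The list item repeats 10.4.3, but it puts the stop where sites make the dosing decision.

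The cost is one clause and one list item. Section 10.4.3, the schedule and the analysis stay as they are.
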